8.1.1. Biological samples

Table 7 summarises the collection of blood in the study. The maximum amount of blood to be collected in the study is ~140 mL per participant.

Table 7 Biological samples

Sample type	Quantity	Unit	Timepoint	Participants sampled
Blood for serum preparation	~10 mL/Visit for antibody determination, ~15 mL for assay standard generation, ~20 mL for safety Screening laboratory assays, ~13.5 mL/Visit for pre/post-vaccination visits safety laboratory assays	mL	As scheduled (refer to Table 1 and Figure 1)	All participants in Step 1 and Step 2

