8.2.2.3. Study holding rules

[Table 11](#) shows the holding rules to be implemented for this study. These holding rules have been written under the assumption that the safety data from all participants will be available. If the data from all participants are not available (e.g., in case a participant is lost to follow-up), then the holding rules will be assessed on a pro-rata basis.

Holding rules 1a-d in all steps of the study and holding rule 2c in Step 1a and 1b will be monitored by the Investigator on a continuous basis (threshold ≥ 1 , refer to [Table 11](#)). Meeting any of these holding rules will trigger a hold of study intervention administration irrespective of number of participants enrolled and/or timing of the event.

For holding rules 2a-b in all steps of the study and holding rule 2c in Step 2, the Investigator will inform IQVIA immediately if a threshold is suspected to be met, without pausing administration of the study intervention (threshold $\geq 2-6$, refer to [Table 11](#)). IQVIA will provide a report to the GVGH PP who will then confirm if the threshold has been met and advise whether to pause the study intervention administration.

If the Investigator becomes aware that a holding rule threshold has been met (either directly or via IQVIA), the following communication sequence must be followed:

- The concerned site staff must put study intervention administration on hold.
- The concerned site staff must immediately inform IQVIA CRA and Medical Monitor (contact details will be provided in a separate document) via email and phone communication who will in-turn inform the GVGH Study Responsible Project Physician.

CONFIDENTIAL

205480 (TYPH-PARATYPH A CONJ VI-CRM O2-CRM GVGH-001 (H02_01TP))
Protocol Amendment 2 Final

- All informed site staff will confirm to their local contact that action has been taken providing appropriate documentation to GVGH through the IQVIA CRA and Medical Monitor.
- GSK will further evaluate the case with the iSRC and GSK Global Safety Board and will take the decision to stop or to restart the study intervention administration. GVGH Project Physician will inform the IQVIA project lead of the decision and the rationale for the decision and all site staff will be informed by IQVIA project lead.

Table 11 Study holding rules

Holding rule	Event	Number of participants needed to pause vaccination in the study and trigger further evaluation by the iSRC		
		Step 1a	Step 1b	Step 2

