1a	Death or any life-threatening SAE regardless of causality	≥1	≥1	≥1
1b	Any non-life-threatening SAE that cannot be reasonably attributed to a cause other than vaccination as per Investigator or Sponsor assessment	≥1	≥1	≥1
1c	Any withdrawal from the study (by Investigator or participant request) following a Grade 3 AE	≥1	≥1	≥1
1d	Any solicited administration-site event or solicited systemic event leading to hospitalisation, OR Necrosis at the injection site, Each with an event onset within the 7-day post-vaccination period	≥1	≥1	≥1
2a	Any Grade 3 solicited administration-site events (lasting 48h or more as Grade 3), with an event onset within each 7-day post-vaccination period	≥3	≥3	≥6
2b	Any Grade 3 solicited systemic events (lasting 48h or more as Grade 3), with an event onset within each 7-day post-vaccination period	≥2	≥2	≥3
2c	Any Grade 3 unsolicited AE, which can be reasonably attributed to the vaccination as per Investigator or Sponsor assessment, with an event onset within each 7-day post-vaccination period OR Any Grade 3 or above abnormality* in pre-specified haematological or biochemical laboratory parameters collected at 7 days post-vaccination period	≥1**	≥1**	≥2

AE=adverse event, SAE=serious adverse event

*Refer to Section 10.9 for the grading scales to the pre-specified laboratory parameters

**The Investigator should inform IQVIA CRA and Medical Monitor immediately if an event occurs and should follow instruction as applicable to holding rules 1a-1d.

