8.3.2.1. Clinically significant abnormal laboratory findings

The Investigator must review the laboratory report, document that he/she did so, and record any clinically relevant changes occurring during the study in the AE section of the eCRF. Clinically significant abnormal laboratory findings are those which are not associated with an underlying disease, unless judged by the Investigator to be more severe than expected for the participant's condition.

- All laboratory tests with clinically significant abnormal values reported during the study should be repeated until the values return to normal/baseline, or until they are no longer considered significantly abnormal by the Investigator. Refer to Section 10.3.6 for more information on clinically abnormal laboratory assessments that qualify as an AE or SAE.
- In case abnormal values are not considered clinically significant by the Investigator, additional evaluations could be requested by the GVGH PP.
- If abnormal values do not return to normal/baseline after an interval judged reasonable by the Investigator, the aetiology of the abnormal value should be identified, and the Sponsor notified.

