10.2.1. Protocol-required safety laboratory assessments

Table 17 shows the protocol-required safety assays, which will be performed by the local laboratory.

Table 17 Protocol-required safety laboratory assessments

Laboratory assessments	Parameters
Safety Screening laboratory assays	
Haematology	
 • Leukocytes (white blood cells [WBC]) • Erythrocytes (red blood cells [RBC]) • Haemoglobin • Haematocrit • Platelets • Eosinophils • Basophils • Neutrophils • Monocytes • Lymphocytes
Clinical chemistry	
 • Total bilirubin • Aspartic aminotransferase (AST) • Alanine aminotransferase (ALT) • γ-Glutamyl transferase (γ-GT) • Lactic dehydrogenase (LDH) • Alkaline phosphatase (AP) • Total proteins • Glucose (random glucose) • Blood urea (BU)* • Creatinine • Sodium • Potassium
Other Screening tests	
 • Hepatitis B surface antigen antibodies • Hepatitis C virus antibodies • HIV antibodies • Prothrombin time • Blood human chorionic gonadotropin (hCG) pregnancy test (for women of childbearing potential)
Pre/Post-vaccination safety laboratory assays (Visit 1, Visit 2, Visit 4, and Visit 5)	
Haematology	
 • Leukocytes (WBC) • Erythrocytes (RBC) • Haemoglobin • Haematocrit • Platelets • Eosinophils • Basophils • Neutrophils • Monocytes • Lymphocytes
Clinical chemistry	
 • Creatinine • AST • ALT • BU*
Other tests	
 • Urine hCG pregnancy test (as needed for women of childbearing potential; required at Visit 1 and Visit 4)

*BU will be converted to blood urea nitrogen for grading purposes. Refer to Section 10.9.

ALT=alanine aminotransferase; AST=aspartate aminotransferase; BU=blood urea; hCG=human chorionic gonadotropin; RBC=red blood cell; SAE=serious adverse event; ULN=upper limit of normal; WBC=white blood cell
NOTES:

All haematology assay outputs should be reported in absolute values.

All events of ALT $\geq 3 \times$ upper limit of normal (ULN) and bilirubin $\geq 2 \times$ ULN ($>35\%$ direct bilirubin) or ALT $\geq 3 \times$ ULN, which may indicate severe liver injury (possible Hy's Law), must be reported as an SAE.

10.3. Appendix 3: Adverse Events: definitions and procedures for recording, evaluating, follow-up, and reporting Definition of AE

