10.3.6. Clinical laboratory parameters and other abnormal assessments qualifying as AEs or SAEs

In the absence of a diagnosis, abnormal laboratory findings assessments (e.g. clinical chemistry, haematology, or other tests) or other abnormal results the Investigator considers clinically significant will be recorded as an AE or SAE, if they meet the definition of an AE or SAE (refer to the Sections 10.3.1 and 10.3.2).

The Investigator must exercise his or her medical and scientific judgement in deciding whether an abnormal laboratory finding, or other abnormal assessment is clinically significant.

All events of ALT $\geq 3 \times$ upper limit of normal (ULN) and bilirubin $\geq 2 \times$ ULN ($>35\%$ direct bilirubin) or ALT $\geq 3 \times$ ULN, which may indicate severe liver injury (possible Hy's Law), must be reported as an SAE.

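### The liver SAE rule reduces to ALT ≥3×ULN alone, labels isolated ALT rises possible Hy's Law, and has no scheduled post-vaccination bilirubin to check the label

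*Protocol*

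**What the plan says.** **The rule.** The notes to Table 17 (Protocol 10.2.1) list two liver findings joined by *or*. The first is ALT ≥3×ULN with bilirubin ≥2×ULN, more than 35% of it direct. The second is ALT ≥3×ULN with nothing attached. The sentence ends: "direct bilirubin) or ALT $\geq 3 \times$ ULN, which may indicate severe liver injury (possible Hy's Law), must be reported as an SAE". Protocol 10.3.6 repeats it, with the same ending: "which may indicate severe liver injury (possible Hy's Law), must be reported as an SAE".

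**The tests.** In Table 17 the screening chemistry panel includes "Total bilirubin • Aspartic aminotransferase (AST" and other analytes. The panel for Visits 1, 2, 4 and 5 is "Creatinine • AST • ALT • BU". Direct bilirubin is in neither panel.

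**Follow-up of abnormal results.** Protocol 8.3.2.1 says: "All laboratory tests with clinically significant abnormal values reported during the study should be repeated". It also lets the sponsor's physician ask for further evaluation when the Investigator does not consider a value clinically significant. Protocol 10.3.9.2 requires the Investigator to do additional tests on any serious event to find its contributing factors. None of these provisions names bilirubin.

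**Consequences of an SAE.** Protocol 9.4.1 makes the percentage of participants with any SAE from Day 1 to Day 197 a primary endpoint. Holding rule 1b in Table 11 has a threshold of one participant in every step and reads: "Any non-life-threatening SAE that cannot be reasonably attributed to a cause other than vaccination as per Investigator or Sponsor assessment". The laboratory part of rule 2c starts at Grade 3. For ALT, Appendix 9 sets Grade 2 at above 2.5 and up to 5×ULN, and Grade 3 above that.

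**The concern.** A rule with two limbs should separate two situations. Here the second limb contains the first, so the bilirubin condition does no work and the Hy's Law label falls on every isolated ALT rise of 3×ULN or more. That label normally marks the combined finding that the first limb describes.

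The label also cannot be tested against the planned measurements, because bilirubin is not measured after vaccination. If a participant did have a combined rise, the event would be reported as an SAE on ALT alone. Whether it was recognised as a combined rise would depend on what the Investigator chose to order, and when. In a first-in-human study that distinction matters to the people reading the safety data, and a transient bilirubin rise could be missed on a later draw.

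**Working it through.** **1. Logic of the rule.** Let A be ALT ≥3×ULN and B be bilirubin ≥2×ULN with more than 35% direct. The rule is (A and B) or A.

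| A | B | (A and B) or A |
|---|---|---|
| no | no | no |
| no | yes | no |
| yes | no | SAE |
| yes | yes | SAE |

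The last column equals A in every row, so B never changes the classification.

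**2. Scheduled bilirubin.** Planned post-vaccination panels: 96 participants × 2 (Day 8 and Day 176) = 192. Panels with total or direct bilirubin: 0. The last scheduled total bilirubin is at screening, Day −21 to Day −1, which is 21 to 1 days before Day 1. On planned days:

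- Day 8 is 7 days after Day 1, so the gap is 1 + 7 = 8 to 21 + 7 = 28 days.
- Day 176 is 175 days after Day 1, so the gap is 1 + 175 = 176 to 21 + 175 = 196 days.

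**3. Grade against seriousness.** ALT from 3 to 5×ULN lies within Grade 2 of Appendix 9, yet the rule makes it an SAE. Compared with the holding rules:

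| | Rule 1b through the SAE rule | Rule 2c, laboratory limb |
|---|---|---|
| ALT level | ≥3×ULN | >5×ULN |
| Causality judgement | yes | no |
| Participants, Steps 1a and 1b | ≥1 | ≥1 |
| Participants, Step 2 | ≥1 | ≥2, reported first without pausing |

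A hold is a pause for review; the column heading in Table 11 reads "Number of participants needed to pause vaccination in the study and trigger further evaluation by the iSRC".

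**4. Effect of one case on the primary SAE percentage** (Clopper-Pearson, the method in SAP 6.1):

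- low-dose investigational group: 1/12 = 8.3% (95% CI 0.2% to 38.5%)
- full-dose investigational group: 1/24 = 4.2% (95% CI 0.1% to 21.1%)

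**5. How often the rule might fire.** The documents give no rate of ALT ≥3×ULN, so the rates below are assumptions. The formula is that of Table 14, 1 − (1 − p)^n. At p = 1% it reproduces the table: 11.4% for n = 12 and 21.4% for n = 24.

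| Assumed rate per participant | At least one among 60 (Step 2) | At least one among 96 | Expected cases, 96p |
|---|---|---|---|
| 0.1% | 5.8% | 9.2% | 0.10 |
| 0.5% | 26.0% | 38.2% | 0.48 |
| 1% | 45.3% | 61.9% | 0.96 |
| 2% | 70.2% | 85.6% | 1.92 |

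Across this range, about two participants or fewer would be expected to need a reflex bilirubin. The point itself does not depend on the rate.

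**The case against.** The strongest reply is that the protocol already forces a work-up. Every ALT ≥3×ULN is an SAE, 10.3.9.2 requires additional tests for every SAE, and 10.3.8.2 requires follow-up until the event is resolved, stabilised or explained. An Investigator who has just reported possible Hy's Law would very probably order bilirubin. This stands, and a reader should not infer that bilirubin would never be measured. What remains is that the test is not named and not tied to the sample in which ALT was raised.

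A second reply is that the reporting hides little. A reader might infer that an ALT-only SAE would be indistinguishable from a clinical SAE at the first interim, which has no individual listings. The SAP does not support that. Section 4.3 produces the final summary tables at the interims. These include unsolicited events by preferred term, with SAEs counted (7.1.3 and 16.1), and biochemistry by grade, treatment and timepoint (16.2). Both would show the ALT rise in its group, although neither links it to the SAE count. The iSRC also reviews unblinded data to 28 days after the first vaccination in Step 2. This reply stands.

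Third, the label feeds no table, endpoint or holding rule, and a true combined rise is still reported within 24 hours. That also stands, and it limits the harm.

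Two further inferences go too far. The SAE rule does not contradict rule 2c: it is a lower trigger with a causality judgement, layered on a higher one without. Nor should the ALT limb be deleted. Together with rule 1b, it lets one unexplained isolated ALT rise pause Step 2 without a separate judgement of seriousness, whereas rule 2c there needs two participants.

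**Conclusion.** The point holds. The rule is logically redundant in both sections and is equivalent to ALT ≥3×ULN. As written it labels isolated ALT rises, including Grade 2 values of 3 to 5×ULN, as possible Hy's Law and makes them mandatory SAEs. One such case moves an investigational group's primary SAE percentage from 0% to 8.3% or 4.2% and, if no other cause is reasonable, meets rule 1b.

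No scheduled post-vaccination test can confirm or remove the label (0 of 192 panels), so a combined rise may not be recognised from protocol-specified tests. The harm is to labelling and recognition, not to reporting: the study is descriptive, the SAE is reported either way, and a hold is a pause for review.

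A reader might infer that a second criterion was lost after the final ALT threshold. The sentence reads that way, but the documents do not say so or indicate what it would be, so none is assumed here. The logic and the panel check rest on the text alone; only the frequencies rest on assumed rates.

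**What to change.** 1. **Confirm intent.** The sponsor states whether a second criterion was dropped from the second limb. If so, restore it in 10.2.1 and 10.3.6 and add its test. Bilirubin would then be needed just to apply the first limb, so the reflex test in item 2 is still required.
2. **Otherwise, reword both sections** to this effect: every ALT ≥3×ULN is reported as an SAE; whenever post-vaccination ALT is ≥3×ULN, total and direct bilirubin are measured on the same sample; the event is called possible Hy's Law only if bilirubin is also ≥2×ULN with more than 35% direct.
3. **Optional.** Add a row to the SAP 16.1 SAE summary for SAEs whose only criterion was an isolated ALT rise. The interim tables already show the ALT rise, and the row would need a derivation rule that the SAP does not now contain.

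The cost is wording in two protocol sections, one instruction to the local laboratory and a few reflex assays. There are no new participants, visits or blood draws. This assumes that the local laboratory can add both bilirubin tests to the existing sample; it already runs total bilirubin at screening.

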10.3.1. Definition of an AE

An AE is any untoward medical occurrence (an unfavourable/unintended sign – including an abnormal laboratory finding), symptom, or disease (new or exacerbated) in a clinical study participant that is temporally associated with the study intervention. The AE may or may not be considered related to the study intervention.

10.3.1.1. Events Meeting the AE Definition

- Significant or unexpected worsening or exacerbation of the condition/indication under study.
- Exacerbation of a chronic or intermittent pre-existing condition including either an increase in frequency and/or intensity of the condition.
- New conditions detected or diagnosed after administration of the study intervention even though they may have been present before study start.
- Signs, symptoms, or the clinical sequelae of a suspected drug, disease, or other interaction.
- Signs, symptoms, or the clinical sequelae of a suspected overdose of either the study intervention or a concurrent medication.
- Signs or symptoms temporally associated with administration of the study intervention.
- Signs, symptoms that require medical attention (e.g., hospital stays, physician visits and emergency room visits).
- Significant failure of an expected pharmacologic or biological action.
- Pre- or post- intervention events that occur as a result of protocol-mandated procedures (i.e., invasive procedures, modification of participant's previous therapeutic regimen).
- Clinically significant abnormal laboratory findings or other abnormal assessments that are present at baseline and significantly worsen following the start of the study will also be reported as AEs or SAEs.

- AEs to be recorded as solicited AEs are described in the Section [10.3.3](#). All other AEs will be recorded as UNSOLICITED AEs.

10.3.1.2. Events NOT Meeting the AE Definition

- Situations where an untoward medical occurrence did not occur (e.g., social and/or convenience admission to a hospital, admission for routine examination).
- Anticipated day-to-day fluctuations of pre-existing disease(s) or condition(s) present or detected at the start of the study that do not worsen.
- Pre-existing conditions or signs and/or symptoms present in a participant before the first dose of study intervention. These events will be recorded in the medical history section of the eCRF.
- Hospitalisation for elective treatment of a pre-existing condition (known or diagnosed before signing the informed consent) that did not worsen from baseline.
- Any clinically significant abnormal laboratory findings or other abnormal safety assessments associated with the underlying disease, unless judged by the Investigator to be more severe than expected for the participant's condition.

10.3.2. Definition of an SAE**An SAE is any untoward medical occurrence that:**

- a. Results in death.

- b. Is life threatening

Note: The term 'life-threatening' in the definition of 'serious' refers to an event in which the participant was at risk of death at the time of the event. It does not refer to an event, which hypothetically might have caused death, had it been more severe.

- c. Requires hospitalisation or prolongation of existing hospitalisation

Note: In general, hospitalisation signifies that the participant has been admitted at the hospital or emergency ward for observation and/or treatment that would not have been appropriate in the physician's office or in an out-patient setting. Complications that occur during hospitalisation are also considered AEs. The event will also be considered serious if a complication prolongs hospitalisation or fulfils any other serious criteria. When in doubt as to whether 'hospitalisation' occurred or was necessary, the AE should be considered serious.

- d. Results in disability/incapacity

Note: The term disability means a substantial disruption of a person's ability to conduct normal life functions. This definition is not intended to include experiences of relatively minor medical significance such as uncomplicated headache, nausea, vomiting, diarrhoea, influenza like illness, and accidental trauma (e.g., sprained ankle) which may interfere or prevent everyday life functions but do not constitute a substantial disruption.

e. Is a congenital anomaly/birth defect in the offspring of a study participant
f. Abnormal pregnancy outcomes (e.g., spontaneous abortion, foetal death, stillbirth, congenital anomalies, ectopic pregnancy)
g. Other situations Medical or scientific judgement must be exercised in deciding whether reporting is appropriate in other situations. Important medical events that may not be immediately life threatening or result in death or hospitalisation but may jeopardise the participant or require medical or surgical intervention to prevent one of the other outcomes listed in the above definition should be considered serious. Examples of such events are invasive or malignant cancers; intensive treatment in an emergency room or at home for allergic bronchospasm; blood dyscrasias; and convulsions that do not result in hospitalisation.

10.3.3. Solicited events

a. Solicited administration-site events

The following administration-site events will be solicited:

Table 18 Solicited administration-site events

All participants
Pain at administration site
Redness at administration site
Swelling at administration site

b. Solicited systemic events

The following systemic events will be solicited:

Table 19 Solicited systemic events

All participants
Fever
Headache
Myalgia (muscle pain)
Arthralgia (joint pain)
Fatigue (tiredness)

Note: participants will be instructed to measure and record the axillary temperature in the evening. If additional temperature measurements are taken at other times of the day, participants will be instructed to record the highest temperature in the diary card.

10.3.4. Unsolicited AEs

An unsolicited adverse event is an adverse event that was either not included in the list of solicited events or could be included in the list of solicited events but with an onset outside the specified period of follow-up for solicited events. Unsolicited AEs must have been spontaneously communicated by a participant who has signed the informed consent. Unsolicited AEs include both serious and non-serious AEs.

Potential unsolicited AEs may be medically attended (i.e., symptoms or illnesses requiring a hospitalisation, or an emergency room visit, or visit to/by a health care provider). The participants will be instructed to contact the site as soon as possible to report medically attended event(s), as well as any events that, though not medically attended, are of participant concern. Detailed information about reported unsolicited AEs will be collected by qualified site personnel and documented in the participant's records.

Unsolicited AEs that are not medically attended or perceived as a concern by the participant will be collected during an interview with the participants and by review of available medical records at the next visit.

